12.1.7 Pregnancy

Before study enrollment, subjects must agree to take appropriate measures to avoid pregnancy. However, should a pregnancy occur in a female study subject, consent to provide follow-up information regarding the outcome of the pregnancy and the health of the infant until 30 days old will be requested.

A female subject or female partner of a male subject must immediately inform the Investigator if she becomes pregnant from the time of consent to 90 days after the last dose of study drug. Any female subjects receiving study drug(s) who become pregnant must immediately discontinue study drug. The Investigator should counsel the subject, discussing any risks of continuing the pregnancy and any possible effects on the fetus.

Although pregnancy itself is not regarded as an adverse event, the outcome will need to be documented. Any pregnancy occurring in a female subject or female partner of a male subject from the time of first dose up until to 90 days after the last dose of study drug must be reported. Any occurrence of pregnancy must be recorded on the Pregnancy Report Form Part I and sent via email or fax to Pharmacyclics Drug Safety, or designee, per SAE reporting timelines. All pregnancies will be followed for outcome, which is defined as elective termination of the pregnancy, miscarriage, or delivery of the fetus. Pregnancies

with an outcome of live birth, the newborn infant will be followed until 30 days old by completing the Pregnancy Report Form Part II and sent via email or fax to Pharmacyclics Drug Safety, or designee, per SAE reporting timelines. Any congenital anomaly/birth defect noted in the infant must be reported as a serious adverse event.

12.1.8 Other Malignancies

All new malignant tumors including solid tumors, skin malignancies and hematologic malignancies will be reported for the duration of study treatment and during any protocol-specified follow-up periods including post-progression follow-up for overall survival. If observed, enter data in the corresponding eCRF.

12.1.9 Serious Adverse Event Reporting (SAE)

12.1.9.1 Definition of an SAE:

An adverse event or suspected adverse reaction is considered "serious" if, in the view of either the investigator, it results in any of the following outcomes:

- Death
- A life-threatening adverse drug experience; this is defined as any adverse
 experience that places the patient, in view of the initial reporter, at immediate risk of
 death from the adverse experience, as it occurred. It does not include an adverse
 experience that, had it occurred in a more severe form, might have caused death.
- Inpatient hospitalization or prolongation of existing hospitalization.
- A persistent or significant incapacity or substantial disruption of the ability to conduct normal life functions.
- A congenital anomaly/birth defect.

12.1.9.2 Important medical events:

Important medical events that may not result in death, be life-threatening, or require hospitalization may be considered a serious adverse drug experience when, based upon appropriate medical judgment, they may jeopardize the patient or subject and may require medical or surgical intervention to prevent one of the outcomes listed in this definition. Examples of such medical events include allergic bronchospasm requiring intensive treatment in an emergency room or at home, blood dyscrasias or convulsions that do not result in inpatient hospitalization, or the development of drug dependency or drug abuse (21)

CFR 312.32). Pregnancy, drug overdose, and secondary malignancy will be handled as SAE. Important medical events as defined above, may also be considered serious adverse events. Any important medical event can and should be reported as an SAE if deemed appropriate by the Principal Investigator

12.1.9.3 SAE reporting:

- All SAEs should be reported to the study nurse or the Principal Investigator [[name]., Ph.D, [contact] or [contact]] within 24 hours of observing or learning of the event.
- All AEs should be reported to the study nurse.
- Expected therapy-related events include those known toxicities or side effects of ibrutinib. These grade 4 or less events, including, but not limited to diarrhea, atrial fibrillation, infection, hemorrhage, hypertension and joint pain/arthralgia will not be reported as individual SAEs, but will be summarized in the annual report to the IRB. However, these will be reported to Pharmacyclics within 24 hours of knowledge of the event.
- Adverse Events Requiring Expedited Reporting: Serious unexpected adverse events (SUSARs) considered associated with therapy should be reported to the study nurse or the Principal Investigator [[name]., Ph.D, [contact] or [contact]] within 24 hours of observing or learning of the event. These events must be reported to the IRB in accordance with the timeframes and procedures outlined in "The University of Texas M. D. Anderson Cancer Center Institutional Review Board Policy for Investigators on Reporting Unanticipated Adverse Events for Drugs and Devices". Unless stated otherwise in the protocol, SUSARs must be reported to the IRB, within 5 working days of knowledge of the event).
- All serious adverse events and AESIs (initial and follow-up information) will be reported on FDA Medwatch (Form 3500A) or Suspect Adverse Event Report (CIOMS Form 1) IRB Reporting Form and sent via email ([contact]) or [contact]) to Pharmacyclics Drug Safety, or designee, within 24 hours of the event.

It is the responsibility of the PI and the research team to ensure serious adverse events are reported according to the Code of Federal Regulations, Good Clinical Practices, the protocol guidelines and Institutional Review Board policy.

12.1.10 Adverse Events of Special Interest (AESI)

Specific adverse events, or groups of adverse events, will be followed as part of standard safety monitoring activities. These events (regardless of seriousness) will be reported on the Serious Adverse Event Report Form and sent via email or fax to Pharmacyclics Drug Safety or designee within 24 hours of awareness.

Major Hemorrhage

Major hemorrhage is defined as any of the following:

- Any treatment-emergent hemorrhagic adverse events of Grade 3 or higher*.
- Any treatment-emergent serious adverse events of bleeding of any grade
- Any treatment-emergent central nervous system hemorrhage/hematoma of any grade

*All hemorrhagic events requiring transfusion of red blood cells should be reported as grade 3 or higher AE per CTCAE v4.03.

Events meeting the definition of major hemorrhage will be captured as an event of special interest according to Section 11.4.6 above.

Investigator Communication with Supporting Companies:

- Any individual expedited SAE reports will be reported to Pharmacyclics.
- All Serious Adverse Events must be reported to Pharmacyclics.
- All SAEs, whether related or unrelated to ibrutinib and all pregnancies must be reported to Pharmacyclics (by the investigator or designee) within 24 hours of knowledge of the events.
- All serious adverse events and AESIs (initial and follow-up information) will be reported on FDA Medwatch (Form 3500A) or Suspect Adverse Event Report (CIOMS Form 1) IRB Reporting Form and sent via email ([contact]) or [contact]) to Pharmacyclics Drug Safety, or designee, within 24 hours of the event. Pharmacyclics may request follow-up and other additional information from the Sponsor Investigator

13.0 CRITERIA FOR REMOVAL FROM STUDY

Criteria for removal from study include, but are not restricted to, the following:

- Clinically significant progressive disease.
- Recurrent non-compliance by the patient with protocol requirements.
- Patient's request to be removed from the study.
- Occurrence of a CTCAE grade 4 non-hematologic adverse event, at least possibly related to ibrutinib. For CTCAE grade 4 adverse events that are numerically defined laboratory parameters, independent investigator assessment should be used to determine the risk:benefit for continuation of therapy.
- Occurrence of an adverse event which makes discontinuation from treatment necessary due to protocol specified safety criteria or desirable in the investigator's and/or the subject's opinion

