16.0 REFERENCES

1.0 OBJECTIVES

1.1 Primary endpoint: Complete remission (CR) or complete remission with incomplete count recovery (CRi) rate at 24 months.

1.2 Secondary endpoints:

- 1. Progression-free survival (PFS) at 2 years.
- 2. Overall response rate (ORR) at 6, 12 and 24 months, CR/CRi rate at 6 and 12 months.
- 3. Time to best response.
- 4. Time to alternative treatment.
- 5. Overall survival at 5 years.

1.3 Exploratory endpoints:

- 1. Effect of ibrutinib treatment on immune function.
- 2. Effect of ibrutinib on frequency of subclonal driver mutations.
- 3. Incidence of emergence of subclonal resistance mutations (e.g. C481S mutation in *BTK* and mutations in *PLCG2*).

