2.0 HYPOTHESES

- 1. We will see a high overall response rate, of approximately 90%, similar to that seen in first line treatment of CLL.
- 2. We anticipate seeing a higher rate of complete remission than in treatment of first-line CLL, given patients will have a lower disease burden. In the early report of a large, phase III study of ibrutinib in the first line setting, the CR/CRi rate was 4%, but this increased to approximately 16% after 2 years of follow-up (Pharmacyclics, internal data). We would expect the CR/CRi rate to potentially double when we treat patients early in their disease course; thus, we anticipate a complete remission rate at 2 years of approximately 30%.
- 3. We anticipate approximately 10-15% of patients will stop therapy due to toxicity. In the phase III study mentioned above, the treatment discontinuation rate was 9% at a median follow-up of 18 months. We expect that in an early treatment population, the rates of discontinuation may be somewhat higher, as there may be less willingness from patients and physicians to tolerate troublesome side effects.
- 4. We anticipate that ibrutinib will have beneficial effects on immune function, including improvement in immunoglobulin levers, including IgA(1) and T-cell function.
- 5. We anticipate a low rate of development of resistance mutations.

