5.0 TREATMENT PLAN

5.1 Recommended prophylactic medications:

The following are recommended prophylactic medications. For individuals who are allergic, an equivalent replacement may be identified:

- Allopurinol 300 mg PO daily for the first 7 days of course 1 is recommended for tumor lysis prophylaxis.
- Valacyclovir 500 mg PO daily for all treatment courses and for at least 3 months after completion of treatment is recommended, for herpes virus prophylaxis.

5.2 Treatment regimen.

Ibrutinib monotherapy will be administered at 420mg once daily until either:

- 1. Disease progression or
- 2. Achievement of complete remission with negative MRD, on two separate assessments, at least 6 months apart. For the purposes of determining treatment cessation, MRD analysis must be performed on bone marrow, using standardized 4-color flow cytometry and demonstrate sensitivity of at least 0.01%.(28) We anticipate a low rate of MRD-negative CR/CRi, which may require prolonged treatment to achieve. Patients who discontinue ibrutinib due to achievement of MRD-negative CR/CRi, will continue to have routine clinical follow-up every 3 months, which will include MRD analysis in peripheral blood, performed at least once per year.
- 3. Completion of 2 years of therapy.

5.3 Long term follow-up.

Patients who remain on therapy at 2 years (the timing of the primary endpoint) may continue ibrutinib, at the discretion of their physician. This would, however, require transition to commercial supply of ibrutinib and should be discussed with the PI. If patients choose to have follow-up at M.D. Anderson, they will be seen every 3-6 months, at the discretion of their physician. If they are receiving follow-up at an outside center, they will be telephoned by study staff every 6 months (until disease progression, death or receipt of a new therapy) to determine:

- Whether they are still receiving study drug.
- Whether any significant toxicity has occurred.
- Whether their disease remains in remission.
- Whether they have had any other cancer therapy.

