- (4) Medical history. Medical and surgical history and demographic information will be recorded. Medical and surgical history includes diagnoses, therapies, and medical and surgical treatments. A complete medical history will be obtained at screening/baseline, prior to first administration of study drug and at the end-of-treatment visit. At all other visits, the medical history taking can be focused to the needs of the patient but should pay particular attention to adverse events that are potentially related to ibrutinib, infections, and disease-related symptoms. During the CoVID19 epidemic, medical history may be obtained by the patient's M.D. Anderson Physician in a telephone or videoconference interview and documented in the chart.
- (5) Physical examination, including vital signs. Vital signs are temperature, pulse, respiratory rate, and blood pressure (when the patient is seated). A complete physical examination, including measurement of weight, must be performed at screening/baseline, prior to the first administration of study drug, and at the end-of-treatment Visit. Height need only be recorded at the initial visit. Following the screening/baseline physical examination, with the exception of the end-of-treatment Visit, all subsequent physical examinations can be focused to the individual needs of the individual patient. Given that, during the CoVID19 epidemic, many patients will not be able to come to M.D. Anderson, some assessments may be conducted remotely. Wherever possible, patients should have a physical exam at least every 6 months and, if unable to come to M.D. Anderson, this should be done by a local physician and the records obtained. If even this is not possible, the reasons for this should be documented in the patient's chart.
- (6) Concomitant medications. These will be recorded in the electronic medical record.
- (7) Complete blood count with differential. CBC with differential is defined as peripheral blood total white blood cell (WBC) count, hemoglobin, hematocrit, platelet count, absolute neutrophil count (ANC), and WBC differential, reported individually for each cell type. Hematologic assessments must be obtained at screening and at every subsequent assessment, as specified in the Schedule of Events, or more frequently as clinically indicated (e.g. to confirm loss of hematologic response as defined in section 9.1).

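### Stopping ibrutinib for toxicity is a criterion for removal from study, and no section follows these patients for progression, alternative therapy or survival afterwards, so 2-year PFS may look slightly too favourable

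*Combined protocol and SAP*

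**What the plan says.** Section 13.0 gives criteria for removal from study, and two of them are toxicity routes: "Occurrence of an adverse event which makes discontinuation from treatment necessary due to protocol specified safety criteria" and "Occurrence of a CTCAE grade 4 non-hematologic adverse event, at least possibly related to ibrutinib". The section does not distinguish leaving the drug from leaving the study.

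Section 2.0, item 3, expects such stops: "We anticipate approximately 10-15% of patients will stop therapy due to toxicity". The comparison offered is a phase III first-line study in which "the treatment discontinuation rate was 9% at a median follow-up of 18 months"; the protocol expects somewhat more in early-stage patients. It attaches no time frame to the 10-15%, but Section 5.2 ends study therapy at "Completion of 2 years of therapy".

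Follow-up off drug is described as follows:

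- Section 5.2 provides three-monthly follow-up for patients who stop because of MRD-negative CR/CRi, and for no other early stoppers.
- Section 5.3, on long-term follow-up, opens with "Patients who remain on therapy at 2 years (the timing of the primary endpoint) may continue ibrutinib, at the discretion of their physician". Its six-monthly calls continue until progression, death or a new therapy.
- Section 10.0 is a schedule during therapy, laid out by cycle, with a column for progression but none for end of treatment or for time off drug. Notes 4, 5, 12 and 13 assume a visit or test at the end of treatment, for example "A complete medical history will be obtained at screening/baseline, prior to first administration of study drug and at the end-of-treatment visit".
- Section 12.1.8 mentions follow-up periods, including survival follow-up after progression, but sets no schedule.

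The secondary endpoints in Section 1.2 include "Progression-free survival (PFS) at 2 years", time to alternative treatment and 5-year overall survival. Section 15.4 names the Kaplan-Meier method and a comparison of each patient's observed with predicted PFS time. It gives no PFS event definition or censoring rule.

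**The concern.** A patient who stops for toxicity at month 8, without progression, fits none of the groups for whom off-drug follow-up is written. Followed literally, Section 13.0 takes that patient out of the study, and the Kaplan-Meier analysis would most naturally censor at that date.

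Kaplan-Meier assumes that censored patients go on to have the same risk as those still observed. That is doubtful here. Entry requires a predicted time to first treatment of 3 years or less (Section 4.1), Section 5.2 anticipates few MRD-negative remissions, and Section 14.2 notes that marrow disease often persists on ibrutinib. Most early stoppers would therefore come off drug with residual high-risk disease.

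The 2-year PFS would then describe ibrutinib while it is taken, rather than a policy of starting it early. The comparison with predicted PFS time would be weakest for the patients in whom early treatment was not sustained. The trial would also hold no data to show whether the loss mattered.

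**Working it through.** **1. The plan's own figure.** Inputs from Sections 15.2 and 15.3: n = 50, null rate 16%, alternative 30%, one-sided exact binomial test at 0.05. P(X ≥ 12 | 0.16) = 0.093 and P(X ≥ 13 | 0.16) = 0.0475, so the test rejects at 13 or more. P(X ≥ 13 | 0.30) = 0.777, which agrees with the stated 78%. Section 11.0 counts a missing response as non-response, so early stoppers without an assessment stay in the denominator. Neither the test nor its stated power depends on PFS follow-up.

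**2. Number affected.** 0.10 × 50 = 5 and 0.15 × 50 = 7.5, so about 5 to 8 patients.

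**3. Possible bias in 2-year PFS.** From the documents: 24-month PFS S = 0.89 (the phase III first-line study in Section 3.5) and stopping fraction d = 0.10 or 0.15. Assumed: a constant hazard on drug, stop times spread evenly over 24 months, and a hazard multiplied by k after stopping. The documents give no value for k, so a range is shown.

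- H = −ln(0.89) = 0.1165.
- PFS at 24 months in stoppers: P(k) = (S − S^k) / ((k − 1)H), with P(1) = S.
- All-patient PFS = (1 − d)S + d·P(k).
- Kaplan-Meier with censoring at stopping estimates S, so the overstatement is d·(S − P(k)).

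| k | P(k) | All patients, d = 10% | All patients, d = 15% | Overstatement (points) |
|---|---|---|---|---|
| 1 | 89.0% | 89.0% | 89.0% | 0 |
| 2 | 84.0% | 88.5% | 88.3% | 0.5 to 0.7 |
| 3 | 79.4% | 88.0% | 87.6% | 1.0 to 1.4 |
| 5 | 71.1% | 87.2% | 86.3% | 1.8 to 2.7 |
| 10 | 55.1% | 85.6% | 83.9% | 3.4 to 5.1 |

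With S = 0.96 (the earlier first-line study in Section 3.5), the overstatement is 0 to 2.3 points over the same range of k.

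**4. Limits with no hazard assumption.** Take 89% as PFS in non-stoppers and let all or none of the stoppers have an event by 24 months. At d = 10% the limits are 0.90 × 0.89 = 80.1% and 80.1% + 10% = 90.1%. At d = 15% they are 0.85 × 0.89 = 75.7% and 90.7%.

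**5. Scale.** The approximate 95% confidence half-width at 89% with 50 patients is 1.96 × √(0.89 × 0.11 / 50) = 8.7 points.

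**The case against.** The best defence is that Section 13.0 is loosely worded and means off treatment. It also lists clinically significant progression as a removal criterion, yet Section 12.1.8 refers to survival follow-up after progression and Section 1.2 has 5-year survival as an endpoint. Removal therefore cannot consistently mean that no further data are collected. Section 11.0 defines progression during or after therapy, and its marrow MRD assessments at 6, 12 and 24 months carry no stated exemption for patients off drug. This stands as evidence of ambiguity. It does not supply a PFS follow-up schedule for toxicity stoppers.

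The later lines of Section 5.3, which ask whether the patient is still receiving drug, could be read more widely, but its opening sentence limits it to patients still on therapy at 2 years.

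It is also true that the affected endpoints are secondary in a single-arm phase II study, that PFS has no success threshold, and that every bias in the table is smaller than the 8.7-point half-width. A confidence interval does not, however, allow for an error that runs in one direction.

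A reader might infer that nothing at all is recorded after the last dose. The documents do not support that: Section 10.0 refers to an end-of-treatment visit and Section 14.1 takes an immune sample on discontinuation. What is missing is follow-up after that point.

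**Conclusion.** The gap is real and of modest size. Section 13.0 read with Sections 5.2, 5.3 and 10.0 leaves toxicity stoppers without follow-up for progression, alternative therapy or survival after the end-of-treatment visit. The effect on 2-year PFS is 0 to about 5 points, and about 0.5 to 1.4 points if the hazard rises 2- to 3-fold off drug. Time to alternative treatment and the comparison with predicted PFS share the problem. The primary endpoint does not.

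Three things are inferred: that removed patients are censored at removal (no rule is stated), that the 10-15% stop before 2 years (from the treatment limit), and that risk rises off drug (if it does not, there is no bias).

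A reader might go further and assume 2-year PFS of 90% in continuers and 50-70% in stoppers. With s stoppers and PFS q among them, ((50 − s) × 0.90 + s × q) / 50 gives 86-88% for s = 5 and 84-87% for s = 7.5, an overstatement of 2 to 6 points. For a stop at month 8, with monthly hazard 0.1054 / 24 = 0.00439, reaching 70% needs (0.3567 / 0.00439 − 8) / 16, about a 4.6-fold hazard, and reaching 50% needs (0.6931 / 0.00439 − 8) / 16, about 9.4-fold. The documents give no off-drug PFS, and the nomogram predicts time to first treatment rather than progression, so they do not support treating 2 points as the floor.

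**What to change.** - **Section 13.0:** state that stopping ibrutinib for an adverse event is discontinuation of study drug and not removal from study. Leave the other removal criteria as they are. This changes what happens to the data, not when treatment is stopped.
- **Follow-up:** keep patients who stop early without progression in follow-up to month 24, using the existing Section 10.0 disease assessments where feasible. At minimum, extend the six-monthly contacts of Section 5.3 to them, and record progression status, outside blood counts or imaging, alternative therapy and survival. The calls as now written ask only whether disease remains in remission, which is thin for dating progression.
- **Section 15.4:** state that PFS is not censored at drug discontinuation.

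The cost is protocol wording plus a few visits or calls for about 5 to 8 patients. The sample size and the 78% power do not change. The downside is that the reported 2-year PFS may be slightly lower.

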14.0 CORRELATIVE STUDIES

- **14.1** Comprehensive analysis of changes in immune function during ibrutinib therapy will be performed. Ibrutinib was shown to inhibit ITK in mice, resulting in skewing of T cell immune responses to a T_H1 phenotype(20) and also enhancing the efficacy of checkpoint blockade with PD-L1 antibodies.(32) We propose a comprehensive immune profiling of CLL patients treated with ibrutinib to understand the possible immunomodulatory effects of this drug. Immune reconstitution studies will be performed on 10-20 ml peripheral blood samples collected from CLL patients prior to initiation of ibrutinib, 3, 6, and 12 months after initiation of ibrutinib therapy and on discontinuation of therapy. We propose to use multi-parameter flow cytometry and *in vitro* functional assays to study T-cell and NK cell numbers, phenotype and function. Testing may include, but not be limited to the following:
 - Analysis of CD4+ and CD8+ T cell phenotype and function including naïve/central memory and effector phenotype (CD45RO, CD62L, CCR7 expression), cytokine profile following T cell receptor engagement and co-stimulation with anti-CD3/CD28 beads including Th1/Th2/Th17 profiles and regulatory T cell frequencies (CD4+CD25+CD127lo,foxp3+).
 - 2. Analysis of antigen-specific T cell responses following stimulation with a viral peptide library pool (Influenza, Cytomegalovirus and Epstein-Barr Virus).

- 3. Assessment of normal B cell reconstitution during ibrutinib therapy by assessing transitional, naïve, switched and IgM memory B cell frequencies (CD24, CD38, CD10, IgM, IgD, CD27). We will perform in vitro studies to look at preferential BTK inhibition in gated normal B cell subsets using Phosflow assays in combination with surface phenotyping.
- 4. NK reconstitution including ratios of CD56dim/CD16+ and CD56bright/CD16lo, expression of activating receptors (NKp30, NKp44, NKp46, NKG2D, NKG2C) and inhibitory receptors (NKG2A and killer immunoglobulin receptors) to assess if ibrutinib impacts NK function and phenotype.
- 5. Cytokine analysis: CCL3, CCL4, IL-4, IL-5, IL-6, IL-10, IL-13, TGF-β, IFN-γ, IL-2, TNF-α.
 - * The assays to perform these studies are set up and routinely performed in the [name]-[name] Laboratories and analysis will be performed by [name].
- **14.2** Ibrutinib has been shown to produce synergistic anti-tumor efficacy with PD-L1 antibodies in mouse lymphoma and other tumor models(32) and to down-regulate PD1/PDL1 on CLL cells and PD1 expression on T cells in peripheral blood. However, the effect of ibrutinib treatment on expression of these immune checkpoint molecules in the marrow, where persistent CLL is frequently seen during ibrutinib therapy, has not been systematically explored. We plan to perform serial assessment of PD-L1, PD-L2 and PD1 by flow cytometry on CLL cells and T cells obtained from both blood and marrow.
- **14.3** Serial analysis of cellular and molecular biomarkers in CLL cells that predict resistance as well as persistence of the disease. A significant proportion of patients with progressive disease were identified to have specific point mutations in *BTK* (C481S) or activating mutations in PLC-γ2 and these mutations appear more common in patients with genomic instability such as those with del(17p) and/or complex metaphase karyotype.(25) We will perform targeted serial deep sequencing using next generation sequencing multiplex panels for known CLL-associated mutations pre-treatment; we will serially monitor the allelic frequency of clonal and subclonal mutations identified at baseline, to identify whether treatment with ibrutinib induces changes in the subclonal architecture. These studies will be performed pre-treatment and at 1, 3, 6, 12 and 24 months from peripheral blood in collaboration with [name] and [name] at Peter MacCallum Cancer Center, Melbourne, Australia. Samples will also be obtained at disease progression.

This sequencing will include serial deep sequencing for BTK and PLC-γ2 mutations, to identify small sub-clones emerging at early time points, whether these expand over time and whether their emergence predicts clinical resistance to therapy.

